7.2.2 Sample Size

The total sample size needed is 20 subjects that are 12 years of age and older. Each subject will be randomized in a 3:1 ratio to receive either the active (15 subjects) or vehicle (5 subjects) product throughout the study. Endpoints will be evaluated using a 2-sided Chi-square test and t-test at the 0.05 significance level.

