4 STUDY POPULATION

4.1 Inclusion Criteria

Subjects who meet all of the following criteria are eligible for this study:

1. Subject is a male or non-pregnant female, 12 years of age and older.
2. Subject is willing and able to provide written informed consent for the study.
3. Subject is willing and able to apply the investigational product as directed, comply with study instructions and commit to all follow-up visits for the duration of the study.
4. Subject has clinical diagnosis of mild to moderate hand dermatitis for at least 3 months.
5. Subject has a baseline Investigator's Global Assessment (IGA) score of 2 or 3 (disease severity of mild or moderate).
6. Subject is in good general health and free of any disease state or physical condition that might impair evaluation of hand dermatitis or which, in the investigator's opinion, exposes the subject to an unacceptable risk by study participation.
7. Women of childbearing potential (WOCBP) must use an effective method of birth control or must be post-menopausal or surgically sterile. Women of childbearing potential (WOCBP) must have a negative urine pregnancy test (UPT) at Baseline.

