5.2 Maintaining the Blind

The subjects will be randomized to receive one of two treatments (active vs. control) in a 3:1 ratio. Thus, out of the total 20 subjects, 15 subjects will receive the active “AFX 5931” medication while 5 subjects will receive the vehicle product. Separate study staff members are assigned to administer the study medication versus conduct study evaluations.

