6.4.2 Visit 2 (Day 0): Baseline

The subject will return to the clinic and will be queried for any changes in health status since the previous visit, including concomitant medications and therapies. A urine pregnancy test with negative result confirmed will be performed for all WOCBP. The Hand Eczema Severity Index and Investigator's Global Assessment will be completed. Baseline reading of local skin reactions will be assessed prior to IP application. The Subject's Local Dermal Tolerability Assessment will be performed. IP will be dispensed to the subject. IP will then be dispensed and subject will apply the first dose in clinic. The subject diary will be dispensed. Digital photographs will be taken at proximal and distal views of both the dorsal as well as palmar surfaces of the subject's hand (treatment area). The subject will be scheduled to return to clinic for Visit 3 in accordance with the treatment window.

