7.2 Statistical Methods

7.2.1 General Statistical Methods

All data collected during the study will be presented in data listings. Summary tables and analyses will be based on the following analysis populations:

Safety population:	All enrolled subjects who received study treatment.
Intention-to-treat (ITT) population:	All enrolled subjects, regardless of whether they received study treatment.
Per protocol (PP) population:	All subjects in the ITT population for whom no major protocol violations occurred.

The primary population for analyses of efficacy data will be ITT population. A supportive analysis will be presented for the PP population if this is significantly different from the ITT population. The assessment of safety will be based on the safety population.

Continuous data will be summarized by treatment group using descriptive statistics (number, mean, median, standard deviation, minimum, and maximum). Categorical data will be summarized by treatment group using frequency tables (frequencies and percentages). Ninety-five percent confidence intervals will be constructed for proportions of successes.

Statistical tests will be used for analysis. The analysis will be 2-sided and conducted at the 0.05 significance level. An analysis of means using an independent samples t-test and ANOVA will be used. Primary analysis will be completed with the help of a chi-square analysis and assessment of relative risk and odds ratios.

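### The 3:1 list is not stratified by baseline IGA and the primary chi-square does not adjust for it: a modest, avoidable loss of precision with 5 vehicle subjects, not a threat to type I error

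*Combined protocol and SAP*

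**What the plan says.** All references are to the Combined protocol and SAP.

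- **Allocation.** Section 7.2.2 Sample Size: "Each subject will be randomized in a 3:1 ratio to receive either the active (15 subjects) or vehicle (5 subjects) product throughout the study". Section 5.2 Maintaining the Blind: "The subjects will be randomized to receive one of two treatments (active vs. control) in a 3:1 ratio". Neither these sections, nor the Synopsis, nor Section 3.2 Overview names a stratum, a block size or minimisation.
- **Entry.** Section 4.1 Inclusion Criteria: "Subject has a baseline Investigator's Global Assessment (IGA) score of 2 or 3 (disease severity of mild or moderate". Baseline IGA is therefore a two-level factor.
- **Timing.** The Synopsis and Section 3.2 place the baseline efficacy readings before product is applied. Section 6.4.2 lists the IGA first and then says: "IP will then be dispensed and subject will apply the first dose in clinic". The grade is therefore known in time to be used for allocation.
- **Analysis.** Section 7.2.1: "Primary analysis will be completed with the help of a chi-square analysis and assessment of relative risk and odds ratios", and "The analysis will be 2-sided and conducted at the 0.05 significance level". Means are compared by t-test and ANOVA. No covariate or stratified test is named.
- **Success.** Section 7.2.1 promises confidence intervals for success proportions, but success is not defined. Section 7.2.8.1 makes changes in HECSI and IGA the primary evaluation.

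**The concern.** On the IGA scale in Section 9.0, a grade 2 subject is one step from almost clear and a grade 3 subject is two steps away. If success means clear or almost clear, the starting grade is a natural predictor of it. With only 5 vehicle subjects, one or two more mild or moderate subjects in that arm make a large change in its make-up. The two arms can then differ in success for a reason unrelated to the product, and neither the allocation nor the planned test takes this into account. A single-centre pilot is read from the one allocation it happens to draw, so the imbalance is not averaged away for the reader.

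**Working it through.** **Inputs from the plan.** N = 20; 3:1 allocation; two-sided 0.05; baseline IGA 2 or 3. The split reproduces: 20 × 3/4 = 15 and 20 × 1/4 = 5. The total of 20 cannot be reproduced, because no power, effect size or response rate is given.

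**Assumed.** The mild/moderate mix (4/16 to 10/10, in either direction) and all success rates.

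**1. Chance imbalance on a single list.** Let m of the 20 be in one grade and k of those m fall in the vehicle arm. Then k is hypergeometric, and the difference in share is d = k/5 − (m − k)/15 = (4k − m)/15, so

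SD(d) = (4/15) × √[5 × (m/20) × (1 − m/20) × 15/19].

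- m = 10: (4/15) × √0.987 = 0.265.
- m = 4: (4/15) × √0.632 = 0.212.

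For the tail at m = 10, |d| ≥ 0.40 needs k = 0, 1, 4 or 5: 2 × (252 + 2100)/15504 = 0.303.

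| Mix | SD of d | P(\|d\| ≥ 40 points) | Worst \|d\| with stratified blocks of 4 |
|---|---|---|---|
| 4/16 | 0.21 | 3.2% | 0 |
| 5/15 | 0.23 | 7.3% | 20 points |
| 6/14 | 0.24 | 26.0% | 13 points |
| 7/13 | 0.25 | 11.4% | 20 points |
| 8/12 | 0.26 | 10.9% | 0 |
| 9/11 | 0.26 | 12.7% | 20 points |
| 10/10 | 0.265 | 30.3% | 13 points |

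The tail probability jumps because only 5 subjects are drawn and 40 points falls exactly on an attainable value at 10/10 and 6/14. The SD is the steadier summary.

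**2. Effect on the success difference.** Assume no drug effect and success of 50% in mild and 20% in moderate subjects, at 10/10. With 4 mild and 1 moderate on vehicle:

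- vehicle (4 × 0.5 + 1 × 0.2)/5 = 0.44;
- active (6 × 0.5 + 9 × 0.2)/15 = 0.32;
- difference −12 points, which is 0.30 × 0.40.

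The mirror case gives +12. With 30%/20% the shift is 4 points; with 60%/20% it is 16.

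**3. Type I error of the planned chi-square.** Under 50%/20% and no drug effect, exact enumeration gives a size of 3.3% to 14.8% conditional on the vehicle mix drawn, but 4.8% averaged over the randomisation. Over three assumed pairs of rates the average is 4.8% to 5.1%.

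**4. What the fix buys at 10/10.** Exact enumeration. The ordinary CMH statistic is T²/V without continuity correction, referred to chi-square on 1 df. The risk difference uses Mantel-Haenszel weights n₁n₀/N in each stratum. The stratified results include the 14:6 and 16:4 outcomes.

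| Assumed success: vehicle mild/moderate; active mild/moderate | Planned chi-square, single list | Stratified list, ordinary CMH | Stratified list, exact CMH | Variance cut (MH difference v crude) |
|---|---|---|---|---|
| 30/10; 70/40 | 26.7% | 27% | 17.1% | 5% |
| 40/10; 80/40 | 27.9% | 29% | 18.5% | 12% |
| 40/5; 85/35 | 31.4% | 36% | 21.9% | 19% |

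The ordinary CMH gains about 1 to 4 points, with null size about 4%. The exact CMH loses 9.6, 9.4 and 9.5 points against the planned test.

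**5. Drift from 15:5.** At 10/10 each stratum ends with a half-filled block that holds its vehicle slot with probability 1/2. So 16:4 and 14:6 each occur with probability 1/4. The mean of 1/n₁ + 1/n₀ is 0.25 × 0.3125 + 0.5 × 0.2667 + 0.25 × 0.2381 = 0.271, against 0.267 at 15:5, about 2% more.

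**The case against.** Randomisation alone makes the comparison valid, and step 3 bears this out. A reader who sees conditional sizes up to 14.8% might infer that the plan inflates type I error. It does not: the average over allocations is close to 5%.

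A reader might also take 30% as the general risk of a badly unbalanced vehicle arm. It is the highest value among the mixes considered, and the plan does not say what mix to expect. Of the seven mixes, only 10/10 and 6/14 exceed 13%.

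Nor do the documents show that baseline IGA drives success. Success is undefined. If it meant a one-grade improvement, the argument from one step versus two would fail. The 30-point gap is an assumption.

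Five vehicle subjects is the larger limit. By normal approximation, power for an assumed 20% v 50% is about 18%, and for 20% v 60% about 31%. Stratifying does not cure that. The data listings would also let a reader see each subject's Visit 2 grade.

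Finally, the plan fixes 15 and 5 in several places, and Section 4.4 works from one sequence of patient numbers and bottles, so stratifying is not free.

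All of this stands. It limits the size of the point but does not remove it: a two-level factor, known before dosing and plausibly prognostic, is left out of both allocation and analysis, and including it needs no extra subjects.

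**Conclusion.** The point holds as an inexpensive improvement in precision and interpretability. It is not a validity flaw. The omission of baseline IGA from the list and from the primary test is plain in the documents. Its consequences rest on assumptions: the mix of grades, a clear/almost clear definition of success, and the gap in success between grades.

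Under those assumptions, a 40-point imbalance has a 3% to 30% chance and moves the success difference by 12 points at a 30-point gap. The full fix at 10/10 saves about 5% to 19% of the variance and adds about 1 to 4 points of power.

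It is tempting to go further and call for an exact stratified test because the arms are so small. The figures do not support that as the primary test: against the plan's own chi-square it costs about 9 to 10 points of power, while the chi-square's average size is already near 5%. The point concerns IGA success only; it does not address HECSI change.

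**What to change.** - **Sections 5.2 and 7.2.2 and the Randomization entry of the Synopsis:** stratify the 3:1 list by Visit 2 IGA (2 v 3) in permuted blocks of 4. State 15 and 5 as planned rather than guaranteed numbers, and state that the number and bottle are assigned after the Visit 2 IGA is scored.
- **Section 7.2.1:** define IGA success. Replace the unstratified chi-square for it with an ordinary Cochran-Mantel-Haenszel test, without continuity correction, and a Mantel-Haenszel risk difference, both stratified by Visit 2 IGA. Do not make the exact version the primary test.
- **If the single list is kept:** use the stratified analysis alone. The gain is then smaller.
- **In either case:** tabulate Visit 2 IGA by arm.

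**Costs.** At 10/10 the final split is 14:6 or 16:4 about 25% of the time each, so vehicle may have only 4 subjects; the variance savings above already include this. Balance is not perfect: the worst residual imbalance is 13 points at some mixes and 20 points at 5/15, 7/13 and 9/11. Two bottle sequences, with spare stock because the mix is unknown, replace the single one in Section 4.4. Fixed blocks of 4 with one vehicle each are somewhat predictable at one centre, so the block size should be kept from site staff.

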Safety Endpoints:	
Safety/tolerability endpoints are monitored by members of the study staff. They include the following:
 
 - Changes in local skin reaction - Changes in AEs and serious adverse events (SAEs) - Changes in vital signs and physical examinations - Changes in concomitant procedures/medications - Presence of signs/symptoms of irritation of the skin.
Statistical Methods:	
 - All analyses of the pooled individual patient data will be performed with the use of SPSS software using a two-way Chi-square test analysis, t-tests, odds ratios, and analysis of variance (ANOVA).
Assessments:	
 - Hand Eczema Severity Index 
 o Investigator-rated: clinical evaluation of both the extent and intensity of hand dermatitis 
 ▪ Clinical signs: erythema, infiltration/papulation, vesicles, figures, scaling, and edema ▪ Locations: fingertips, fingers (excluding tips), palms of hands, backs of hands, wrists ▪ Extent is graded on a visual 5-point scale ▪ Intensity is graded on a visual 4-point scale - Local Skin Reaction Assessment 
 o Investigator-rated: clinical grading score of erythema, induration/papulation, and lichenification 
 ▪ Each parameter is graded on a visual 4-point scale - Subject's Local Dermal Tolerability Assessment: 
 o Subject-Rated: clinical grading score of pruritus 
 ▪ Each parameter is graded on a visual 4-point scale - See assessments reference at end
Randomization:	
 - The subjects will be randomized to receive either the active or control medication based on a 3:1 randomization scheme - Out of 20 total subjects, 15 will receive the active treatment while 5 will receive the vehicle
Photography:	
 - Digital photographs will be taken at proximal and distal views of the dorsal as well as palmar surfaces of the hand

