7.2.8 Efficacy Analyses

Efficacy variables will be analyzed at the time points shown in the visit schedule.

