7.2.8.1 Primary Efficacy Analyses

This study is concerned with the efficacy of topical AFX 5931 in the treatment of mild to moderate hand dermatitis. Changes in clinical scores recorded via the Hand Eczema Severity Index and Investigator's Global Assessment will be the primary modes of efficacy evaluation.

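### The primary score, visit and success definition are not fixed, so the chi-square analysis named as primary cannot be run without a cut-point that the plan does not give

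*Combined protocol and SAP*

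**What the plan says.** - **Scores.** Section 3.1 lists HECSI and IGA under the primary objective, and section 9.0 puts both among the primary endpoint evaluations. Section 7.2.8.1 names as the primary evaluation "Changes in clinical scores recorded via the Hand Eczema Severity Index and" the IGA. Nothing ranks one above the other.
- **Visits.** Section 7.2.8: "Efficacy variables will be analyzed at the time points shown in the visit schedule". The schedule in section 6.3 has both scores at Day 14 and Day 28 after baseline. Neither is called primary.
- **Tests.** Section 7.2.1 provides a t-test and ANOVA for means, then says: "Primary analysis will be completed with the help of a chi-square analysis and assessment of relative risk and odds ratios". Section 7.2.2 adds: "Endpoints will be evaluated using a 2-sided Chi-square test and t-test at the 0.05 significance level".
- **Success.** Section 7.2.1: "Ninety-five percent confidence intervals will be constructed for proportions of successes". No section gives an IGA cut-off or a HECSI response threshold.
- **Population.** This is settled: "The primary population for analyses of efficacy data will be ITT population".
- **Multiplicity.** Section 7.2 has no rule.

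**The concern.** A primary analysis should give one answer to the primary objective. Here the stated variable is a change in score, while the stated primary analysis needs each subject classed as a success or a failure. Someone has to supply the step between the two. If that happens after unblinding, the score, visit, cut-point and form of chi-square are all open to choice with the results in view. The reader of the report then could not tell which p-value was the planned one, or whether 0.05 describes its error rate.

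**Working it through.** **1. The plan's own figure.** 20 × 3/4 = 15 active and 20 × 1/4 = 5 vehicle, as section 7.2.2 states. The total of 20 cannot be re-derived, because no power, effect size or response rate is given. It is not at issue here.

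**2. Does the cut-point matter?** Baseline IGA is 2 or 3 (section 4.1, criterion 5). Take two ordinary definitions of success:
- A change from 3 to 2 fails under IGA 0 or 1, but succeeds under at least 1 grade better.
- A change from 2 to 1 succeeds under both.

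An illustration with assumed figures: half the subjects start at IGA 3 and, at either baseline, 45% improve by 1 grade and 15% by 2.
- At least 1 grade better: 45% + 15% = 60%.
- IGA 0 or 1: those starting at 2 need 1 grade (60%) and those starting at 3 need 2 grades (15%), so 0.5 × 60% + 0.5 × 15% = 37.5%.

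The same data give 60% or 37.5% success.

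**3. Error rate if any significant result counted.** The plan does not state this rule; the figures show only what the open wording could allow. Four independent 2-sided 0.05 tests would give 1 − 0.95^4 = 18.5%. The scores are correlated, so the tests were simulated: 60,000 trials per setting with no true effect, 15 against 5 subjects, normal change scores for HECSI and IGA at Day 14 and Day 28, and correlations between scores and between visits each from 0.3 to 0.9. The correlations are assumptions.
- One t-test: 2.5% favouring active, 5% in either direction.
- Four t-tests (2 scores × 2 visits): 5-9% favouring active, about 10-18% in either direction.
- Both scores required to be significant, t-tests at Day 28: 0.2-1.5% favouring active.

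On the narrower reading of chi-square at Day 28 only, exact enumeration of one uncorrected test at 15 against 5 gives 0.0, 0.1, 1.4 and 2.6% favouring active at success rates of 10, 20, 35 and 50%. With Yates' correction the figures are 0.0, 0.0, 0.2 and 0.5%. Testing both scores can at most double these. That is about 5% uncorrected at the 50% rate (2 × 2.6% = 5.2%), little above 2.5% at 35% (2 × 1.4% = 2.8%), far below it at the lower rates, and about 1% at most with Yates.

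**4. Does the version of the test matter?** With s successes among 20, the expected vehicle counts are 5s/20 and 5(20 − s)/20. They add to 5, so both are below 5 whenever both outcomes occur. Take 9/15 against 0/5, with expected vehicle counts of 2.25 and 2.75:
- Uncorrected: 20 × (9×5 − 6×0)² / (15×5×9×11) = 40,500/7,425 = 5.45, p = 0.020.
- Yates: 20 × (45 − 10)² / 7,425 = 24,500/7,425 = 3.30, p = 0.069.
- Fisher: [C(11,5) + C(9,5)] / C(20,5) = (462 + 126)/15,504 = 0.038.

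The plan does not say which version applies.

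**The case against.** The strongest reply is that section 7.2.1 can be read sensibly: t-test for means, chi-square for proportions. That is the natural reading, and it stands. A reader might infer that chi-square is simply the wrong test. The documents do not support that, because it works once success is defined. What is missing is the definition, and a statement of which analysis is primary for a variable described as a change in score.

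A reader might also take section 7.2.2 to put both tests on every score at every visit, eight in all, and quote a larger error rate. That reading is strained. Section 7.2.1 separates means from proportions, and a chi-square on HECSI would need a threshold that no section gives. Nor does the plan say that any one significant result would establish efficacy. It only fails to rule this out.

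The simulation has limits. IGA change takes few values but was treated as continuous, and correlations near 0.3 may be low for two scores of the same hands. The upper ends of the ranges depend on those low values.

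Finally, this is a 20-subject pilot with no power claim. That limits the consequence: estimates, confidence intervals and listings stay usable. It does not remove the gap, because the plan commits to a primary analysis and 2-sided 0.05 tests. Section 8.2 refers to methods described in an SAP, but section 7.2 is the only statistical text in the document supplied.

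**Conclusion.** The point holds and should be fixed. Two unranked primary scores, two unranked visits, no multiplicity rule and an undefined success mean that the primary analysis cannot be run as written without a choice the plan leaves open. Taking any significant t-test as success would raise the chance of a false result favouring active from 2.5% to 5-9% (from 5% to about 10-18% in either direction), given assumed correlations of 0.3-0.9. On narrower readings there is little or no inflation, so it would be wrong to say that the plan as written has an inflated error rate. The firm finding is that the error rate is undetermined until one reading is fixed. Separately, the unstated version of the chi-square can by itself move a result across 0.05. The analysis population is specified and is not part of this criticism.

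**What to change.** Before unblinding, amend sections 7.2.1, 7.2.2 and 7.2.8.1:
- Name one primary score, visit and test in the ITT population. Example: change from baseline in total HECSI at Day 28, with one 2-sided 0.05 test of means.
- Make IGA success at Day 28 secondary, with the cut-point written down in advance (for example IGA 0 or 1), and compare it by Fisher's exact test.
- If both scores stay primary, require both to be significant or split the 0.05 between them.
- Label Day 14 and all other p-values exploratory.

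The cost is wording only: no extra subjects, visits or data. The downside is that only one result can be called significant. Fisher's test is also conservative at 15 against 5: by exact enumeration its 2-sided size is at most about 2.5%, reached at a 50% success rate.

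A separate inconsistency bears on the Day 14 data. Section 3.2 calls Day 14 a telephone call, while the synopsis study design lists a follow-up and sections 6.3 and 6.4.3 schedule HECSI and IGA scoring there, at a clinic visit under 6.4.3. These sections must be reconciled.

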7.2.3 Interim Analyses

An Interim Analyses is not applicable.

7.2.4 Missing Data

Missing data will be left blank.

7.2.5 Patient Disposition

The numbers and percentages of enrolled subjects who completed the study and discontinued from the study will be provided, as well as reasons for earlier discontinuation.

